3.3 Summary of Study Design

This is a Clinical, pre-market open label, non-randomized, prospective, single-site, non-blinded, research study, that will enroll from the accessible adult (aged >18 years) female population in the 2nd and 3rd trimesters of pregnancy. The study will be conducted in two stages, beginning with a run-in study (Part 1), followed by a clinical study (Part 2). The results of the run-in pilot study will not be included in the results and data analysis; rather, Part 1 of this study will be used to test procedures and determine any experimental factors that have yet to be defined. The study will be conducted at a GE-operated facility. The study is expected to last approximately 6 weeks. The study is not statistically powered for any measure, and is intended to evaluate procedural accuracy of the Vscan Access R2 Ultrasound System Assisted FHR versus use of a conventional FHR monitor (reference): GE Corometrics* 170 Series Fetal Monitor.

4. STUDY DESIGN

4.1 Study Population

Adult women (aged >18 years) in their 2nd or 3rd trimesters of pregnancy based on self-report, will be enrolled. A normal FHR usually ranges from 120 to 160 beats per minute (bpm). FHR rises through early pregnancy, peaking at 170 bpm (10 weeks), and then, decreases through the 2nd trimester (~140 bpm by 20 weeks), until the end of the 3rd trimester (130 bpm at term).¹⁹ This population of subject selected are feasible for the collection of representative FHR ultrasound scans, within a range suitable for validating the feasibility and accuracy of the

Vscan Access R2 Ultrasound System, with Assisted FHR versus the conventional, commercially available GE Corometrics* 170 Series Fetal Monitor.

4.2 Number Subjects

Up to 25 subjects will be included as part of this study to achieve the targeted number of complete and evaluable subjects. The target sample size for this study is 15 subjects. This includes testing up to 5 subjects in Part 1 and 20 subjects in Part 2 of the study. The sample size for both study parts is based on estimation necessary for study device evaluation and validation requirements. This study is not statistically powered for any measure.

There is only a single population under study, which is intended to include a range of clinical cases representative of FHR exams conducted at a typical site. This protocol does not prospectively specify any quotas based on scan type or anatomy. However, the site should attempt to enroll a diverse range of subjects including race, ethnicities, and anatomies in order to test a range of features on the study device.

4.3 Protection of Vulnerable Subjects

Vulnerable subjects are individuals whose willingness to volunteer in a clinical investigation could be unduly influenced by the expectation, whether justified or not, of benefits associated with participation or of retaliatory response from senior members of a hierarchy in case of refusal to participate.

The Sponsor shall avoid improper influence on, or inducement of, the subject, monitor, any investigator(s), or other parties participating in, or contributing to, the clinical investigation.

All investigators shall avoid improper influence on, or inducement of, the subject, Sponsor, monitor, other investigator(s), or other parties participating in, or contributing to, the clinical investigation.

The study activities cannot otherwise be performed without the use of vulnerable populations because FHR can only be measured in pregnant women with viable fetuses.

Pregnant women/fetuses/neonates: Pregnant women, fetuses, and/or neonates will be subjects in this study. The purpose of this study involves meeting the health needs of these populations. The mother and the fetus will be placed at risk only to the minimum extent necessary to meet such needs, and risk to the fetus will be minimal.

4.4 Eligibility Criteria

4.4.1 Inclusion Criteria

All included subjects will be:

1. Women aged 18 years or older at the time of consent;
 2. By self-report, are in the 2nd or 3rd trimester of pregnancy;
- AND
3. Able and willing to provide written informed consent for participation.

4.4.2 Exclusion Criteria

Subjects will be excluded that:

1. Are direct employees/contractors of General Electric (GE);

2. Have anatomical characteristics or comorbid medical conditions that prevent completion of ultrasound scanning using the study device;
- OR
3. Are potentially put at additional risk by participating, in the opinion of study staff.

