
Procedures/ Methods:
	
Subjects in the initial pilot period (Part 1) and validation testing (Part 2) will undergo up to 45 minutes of ultrasound scanning, including up to 8 test scans on the Vscan Access R2 Ultrasound System with Assisted FHR (research device) and a conventional commercially available ultrasound device. Subjects will also undergo routine commercially available noninvasive FHR monitoring as a reference. All procedures will be conducted at a Sponsor, GE Healthcare (GEHC), facility. All members of the study staff will be qualified based on experience and trained prior to participation.
 
The study population will consist of asymptomatic women ages 18 or older in the second (2nd) and third (3rd) trimesters of pregnancy. Users will be instructed to use the VScan Access R2 device to take a 3 second video of the volunteer, which will result in a calculated fetal heart rate measurement from the monitor. Volunteers will also undergo routine commercially available FHR monitoring using the current standard of care.
 
The first session (Part 1) will be a run-in session, in which the parameters and procedures will be a replica of the study but these results will not count towards the documented results. There will be four (4) sessions following this run-in session (Part 2). Each of these sessions will be approximately 3-4 hours in length over a period of 1-2 weeks.
 
In each session, there will be 1-2 users and 3 volunteers. The users will be instructed to take as many measurements as possible during the allotted time. Finalization of the procedure to calculate accuracy is to be determined based on the run-in procedures executed in Part 1. The specific procedures for the measurement of accuracy which will be used for validation will be performed by the team during Part 1 of the study.

Objectives:
	
Data from Part 1 and Part 2 may be pooled or analyzed as separate subgroups, as determined necessary by the sponsor.
 
The primary objective is to validate the accuracy of the VScan Access R2 ultrasound assisted FHR measurement compared to the reference standard in a pregnant population.
 
The exploratory objective is to collect usability data for further user experience optimization.
 
The safety objective is to collect safety information, including type and number of AEs, SAEs, and other device issues.

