3. STUDY OBJECTIVES AND ENDPOINTS

3.1 Purpose of the Study

The purpose of the study is to evaluate the procedural accuracy of the Vscan Access R2 Ultrasound System with Assisted FHR feature, versus the use of a conventional FHR monitoring device, such as GE Corometrics* 170 Series Fetal Monitor, for measuring FHR in pregnant women in the 2nd and 3rd trimesters. The Vscan Access R2 Assisted FHR method is an innovative way of assessing FHR that is semi-automated and does not involve any

manual measurements once the fetal heart is scanned, unlike conventional methods of measuring FHR with M-mode ultrasound.

3.1.1 Primary Objective:

- To validate the accuracy of the Vscan Access R2 Ultrasound System Assisted FHR measurement compared to the reference standard in a pregnant population.

3.1.2 Exploratory Objective(s):

- To collect usability data for further user experience optimization.

3.1.3 Safety Objective(s):

- To collect safety information, including type and number of AEs, SAEs, and device issues.

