3.2 Study Endpoints

3.2.1 Primary Endpoints:

- FHR data from the investigational and comparator devices on a per-sample basis in bpm (beats per minute)

3.2.2 Exploratory Endpoints:

- The number of subject cases containing scan parameters will be reported and descriptively summarized as necessary to assist in evaluation and optimization of the Vscan Access R2 Ultrasound System.

3.2.3 Safety Endpoints(s):

- Type and number of AEs, SAEs, and device issues.

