4.5 Recruiting and Screening

Subjects will be recruited for potential enrollment in this study according to the standard procedures of the investigational site, unless otherwise specified by the Sponsor in this study protocol. All participation will be voluntary. During subject recruitment, efforts will be made to identify subjects with variety of gestational age and number, race and ethnicity, age, and body type. Recruiting materials may target necessary subpopulations.

Subjects will be screened for enrollment in this study against the inclusion and exclusion criteria according to the standard procedures of the investigational site.

Following recruitment, a subject will be considered enrolled (the point of enrollment) once she signs and dates the informed consent form (ICF). Once enrolled, the subject will be assigned a unique subject number, which will not contain information that could identify the subject (such as subject name or date of birth). The unique subject number will be used to label case report form (CRF) data for the subject throughout his/her participation in the study.

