4.6 Criteria for Withdrawal/Discontinuation

A subject may withdraw from study participation at any time, for any reason. The study staff may withdraw a subject at any time, for any reason. The reasons for withdrawal and discontinuation for any subject shall be recorded to the Sponsor-provided case report form (CRF). Subjects may be withdrawn if they require medications (such as sedatives) that could interfere with study participation. These will be reported to the Sponsor. The IRB should be notified per their notification of subject withdrawal policy.

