5.7 Subject Procedure

Subjects will be asked basic demographic and pregnancy status questions. Subjects will be screened for eligibility and no other preparations are required to participate. Following consent, eligible subjects will be fitted with a conventional FHR Monitor while simultaneously undergoing a non-invasive abdominal ultrasound scan using the Vscan Access R2 system with Assisted FHR and a commercially available ultrasound device (reference standard). FHRs will be collected using both devices.

Eight (8) paired ultrasound scans with FHR Monitor determination will be attempted for each subject participating in the study (a total of 16 scans each, 8 with the research device and 8 with the reference device). Each paired scan will last approximately 5 minutes for both determinations, for a total of approximately 40 minutes of total ultrasound exposure. Breaks may be provided between scans based on operator availability or requests by the subject. At least 2 operators will perform scanning for each subject.

A prospective blocked schedule detailing the order in which scanning will be conducted for each operator and subject will be prepared before the start of subject scanning.

Up to 5 clinicians (Experienced sonographers, Novice users e.g. newly qualified sonographers, nurses/midwives, etc.) - with an approximate 80-20 split of novice vs. experienced - with respect to ultrasound familiarity & scanning experience will be aspired for.

The resultant ultrasound and case data (including basic demographics; self-reported pregnancy status; and information about when and how the ultrasound exam was conducted) will be collected for each subject.

All procedures will be conducted at a Sponsor, GE Healthcare (GEHC), facility. All members of the study staff will be qualified based on experience and trained prior to participation.

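### Exclusion criterion 2 depends on the device under test, so hard-to-scan women can be left out and Vscan non-completion has no required count

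*Combined protocol and SAP*

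**What the plan says.** Section 4.4.2, repeated in the synopsis, excludes subjects that "Have anatomical characteristics or comorbid medical conditions that prevent completion of ultrasound scanning using the study device". The synopsis identifies the research device as the Vscan Access R2 with Assisted FHR. The criterion mentions neither the reference device nor ultrasound in general.

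The primary objective in section 3.1.1 is "To validate the accuracy of the Vscan Access R2 Ultrasound System Assisted FHR measurement compared to the reference standard in a pregnant population". Section 4.2 describes a single population "intended to include a range of clinical cases representative of FHR exams conducted at a typical site", and section 4.5 adds that "efforts will be made to identify subjects with variety of gestational age and number, race and ethnicity, age, and body type".

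On sequence, section 4.5 screens women against the criteria and counts them as enrolled at consent. Section 5.7 says "Subjects will be screened for eligibility and no other preparations are required to participate", after which eligible women are fitted with the monitor and scanned. No screening scan is described. Section 4.6 adds that "The study staff may withdraw a subject at any time, for any reason" and requires the reason to be entered on the CRF.

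The primary endpoint (section 3.2.1) is the FHR value from each device, per sample, in bpm. Section 10.8 promises a summary of disposition and of the number of image sets collected. Section 10.9 rules out imputation.

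**The concern.** An accuracy study should choose its subjects without reference to how the index device performs in them. Here the condition for exclusion is that the index device cannot be used to completion. The women most likely to be affected are at the difficult end of the body-type and anatomy range that sections 4.2 and 4.5 say the study wants to cover.

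Two things are at stake. The first is whom the accuracy result describes: a pregnant population seen at a typical site, or the part of it in whom the Vscan can be used. The second is whether a reader of the final report could learn how often the Vscan could not be used. That matters for a device whose stated rationale includes basic screening by novice users.

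**Working it through.** The plan states no completion or failure rate, so there is no figure of its own to reproduce. The check is a reading of the text, followed by an illustration on assumed rates.

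**1. When is criterion 2 judged?** Sections 4.5 and 5.7 place screening before scanning, so the natural reading is a judgement made in advance. No rule says how that judgement is made without a scan, and whether anatomy prevents a Vscan scan may become clear only on trying. No section says that eligibility is closed once scanning starts. Two routes are therefore open: exclusion by prior judgement, or removal after a failed attempt. The protocol does not say which applies.

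**2. What does the criterion cover?** Only non-completion of scanning due to anatomy or comorbidity. Operator and software failures fall outside it, and fetal position is not clearly inside it. Completing a scan is also not the same as obtaining an Assisted FHR reading: the synopsis describes a 3-second video from which the device then calculates the rate.

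**3. Is the loss recovered elsewhere?**
- Section 1.3: the only named bias control is consecutive enrolment of eligible subjects, so it acts after criterion 2.
- Section 3.2: no completion or failure endpoint.
- Section 6.7: images are saved for subjects who complete a scan.
- Section 10.8: image sets are counted, but no number of attempted scans is named as a denominator and no screen-failure log is mentioned.
- Section 4.6: withdrawal reasons are recorded, so an enrolled woman who is removed leaves a trace.

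**4. Illustration.** Let f be the proportion of otherwise eligible women in whom Vscan scanning cannot be completed. The documents do not give f; 2% to 20% is assumed. The sample sizes are 15 (the target, and the Part 2 maximum in Table 1) and 20 (the Part 2 figure in section 4.2).

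Expected number = n × f. P(at least one) = 1 − (1 − f)^n.

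| f (assumed) | Expected, n = 15 | P(at least one), n = 15 | Expected, n = 20 | P(at least one), n = 20 |
|---|---|---|---|---|
| 2% | 0.3 | 26% | 0.4 | 33% |
| 5% | 0.75 | 54% | 1.0 | 64% |
| 10% | 1.5 | 79% | 2.0 | 88% |
| 20% | 3.0 | 96% | 4.0 | 99% |

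If criterion 2 catches a share c of these women, the rate seen among those who remain is f(1 − c)/(1 − fc).
- c = 1: 0%, whatever f is.
- c = 0.5, f = 10%: 0.05/0.95 = 5.3%.
- c = 0.5, f = 20%: 0.10/0.90 = 11.1%.

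Even without selection, zero failures would be weak evidence. The one-sided 95% upper bound is 1 − 0.05^(1/n), which is 18.1% for n = 15 and 13.9% for n = 20. With criterion 2 in force, that bound would not apply to the intended population.

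**5. Effect on bpm agreement.** A woman with no Vscan reading contributes no pair whether she is kept or removed, so for her the paired accuracy result is unchanged. A woman left out by prior judgement who would have given some readings does take pairs with her. The documents give nothing from which to derive how those pairs would have agreed.

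**The case against.** The strongest reply is that the written sequence is screening, consent and then scanning of eligible women, and that no section reclassifies anyone afterwards. A reader might infer that Vscan failures are turned into ineligible subjects as a matter of course. The text does not say so; it only fails to prevent it. Nor does a woman who is scanned without yielding a reading clearly meet the criterion.

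Safeguards also exist. A consented woman is enrolled and numbered, her withdrawal reason is recorded, disposition is summarised, and data collected before withdrawal may still be used (section 5.9). Device deficiencies, which by the definition in section 8.7 include inadequate performance, are to be documented (section 8.10), and device issues form a safety endpoint. These points stand, and they rule out any claim that cases vanish without trace. None of them requires non-completion to be counted against attempts or shown beside the accuracy result, and a woman excluded before consent may leave no record.

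A reader might also infer that the report will show near-complete acquisition by construction. If, say, 2 of 15 women failed, keeping them gives 13/15 = 87% with a reading and removing them gives 13/13 = 100%. Those counts are invented, and the protocol defines no acquisition rate, so the comparison shows the direction of the effect and is not a forecast.

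Finally, the study is descriptive and unpowered. That limits what it can claim, but selection that favours the device does not depend on power.

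**Conclusion.** The point holds in a limited form. Criterion 2 lets the performance of the device under test decide who is studied, which conflicts with the objective in section 3.1.1 and the sampling aims in sections 4.2 and 4.5. The consequences are a case spectrum that can be narrowed towards women in whom the Vscan works, and no required count of Vscan non-completion.

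The size of the effect is not known. The 26% to 96% chance that 15 unselected women include at least one affected woman rests wholly on an assumed rate of 2% to 20% and on treating women as independent. The documents do not support a stated bias in bpm agreement, and they do not show that the criterion will in fact be applied after failed scans. The change is worth making because it is cheap and alters what the study can conclude.

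**What to change.** In section 4.4.2 and the synopsis, reword criterion 2 so that it does not refer to the study device and is judged before the first scan, for example a known condition that precludes any abdominal ultrasound examination. Leave criterion 3, and voluntary or safety withdrawal, as they are.

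State that a woman is not reclassified as ineligible once scanning has started. In section 10.8, report Vscan non-acquisition per subject and per attempted scan, with the reason and whether the reference obtained a reading, beside the paired accuracy result.

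The cost is a few sentences and an addition to the disposition summary. The reported result may be less favourable. Women without readings may also use places within the enrolment cap without adding pairs: at 8 pairs per woman, 15 women give at most 120 pairs, and two women without readings would reduce that to 13 × 8 = 104.

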4.5 Recruiting and Screening

Subjects will be recruited for potential enrollment in this study according to the standard procedures of the investigational site, unless otherwise specified by the Sponsor in this study protocol. All participation will be voluntary. During subject recruitment, efforts will be made to identify subjects with variety of gestational age and number, race and ethnicity, age, and body type. Recruiting materials may target necessary subpopulations.

Subjects will be screened for enrollment in this study against the inclusion and exclusion criteria according to the standard procedures of the investigational site.

Following recruitment, a subject will be considered enrolled (the point of enrollment) once she signs and dates the informed consent form (ICF). Once enrolled, the subject will be assigned a unique subject number, which will not contain information that could identify the subject (such as subject name or date of birth). The unique subject number will be used to label case report form (CRF) data for the subject throughout his/her participation in the study.

4.6 Criteria for Withdrawal/Discontinuation

A subject may withdraw from study participation at any time, for any reason. The study staff may withdraw a subject at any time, for any reason. The reasons for withdrawal and discontinuation for any subject shall be recorded to the Sponsor-provided case report form (CRF). Subjects may be withdrawn if they require medications (such as sedatives) that could interfere with study participation. These will be reported to the Sponsor. The IRB should be notified per their notification of subject withdrawal policy.

5. STUDY PROCEDURES

5.6 Study Parts

The study will be conducted in two parts, including a initial pilot run-in period (Part 1) and testing period (Part 2), as described in Table 1. Patients in both parts of the study will undergo the same procedure and have a similar experience in the study; however, results will not be collected or recorded for analysis from Part 1 of the study

Table 1 - Description of Study Parts

Study Part	Maximum enrollment	Operator Experience Level	Description
Part 1	5	Any experience level	Pilot for determining
Part 2	15	Approx. 4 Novice and 1 Experienced	Scanning with fixed parameters

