GEHC	General Electric Healthcare
ICF	Informed Consent Form
ISO	International Standards Organization
MWS	GE MyWorkshop Internal Documentation System
PRTS	Protocol synopsis
SADE	Serious Adverse Device Effect
SAE	Serious Adverse Event
SPR	System Problem Report
US	United States
U/S	Ultrasound
USADE	Unexpected Serious Adverse Device Effect

STUDY SYNOPSIS	
Sponsor:	General Electric Company, acting through its GE Healthcare Business
Research Type:	This is a clinical, open label, non-randomized, prospective, single-site, non-blinded research study, that will enroll from the accessible women (aged >18 years) in the 2nd and 3rd trimesters of pregnancy. The study will be conducted in two parts, including an initial pilot for determination of parameters (Part 1) and continued testing (Part 2).
Regulatory Status:	This is a pre-market research study of the following products: Pre-market: Vscan Access R2 Ultrasound System Post-market: GE Corometrics* 170 Series Fetal Monitor
Background and Rationale:	Fetal heart rate (FHR) estimation is an important tool for assessment of fetal well-being and development during pregnancy that is traditionally measured using M-mode or Doppler methods on ultrasound systems. The Vscan Access Ultrasound system is a diagnostic ultrasound imaging system manufactured by the study Sponsor, GE Healthcare (GEHC) and equipped with Assisted FHR, a novel investigational feature that enables visualization and measurement of fetal heart rate. This feature visually maps obstetrical and abdominal anatomical structures and fluid and is intended to be used by qualified and trained primary and specialty health care professionals, including midwives, other paraprofessionals and general physicians. The built-in preset workflows and protocols, particularly enable novice users to scan efficiently and conduct basic screening exams. This technology provides an innovative way of assessing FHR that is semi-automated and does not involve any manual measurements once the fetal heart is scanned. This study is being conducted to validate procedural accuracy of the Vscan Access R2 Ultrasound System with Assisted FHR Measurement in users of all experience levels.

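### The protocol contradicts itself on whether Part 1 data are recorded and usable, and requires no documented Part 1 basis for the parameters and accuracy calculation that Part 1 must settle

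*Combined protocol and SAP*

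**What the plan says.** **What Part 1 is for.** The synopsis (Research Type) describes Part 1 as the pilot in which parameters are determined. The synopsis (Procedures/Methods) adds: "Finalization of the procedure to calculate accuracy is to be determined based on the run-in procedures executed in Part 1". Section 3.3 says: "Part 1 of this study will be used to test procedures and determine any experimental factors that have yet to be defined". Table 1 then has Part 2 run with fixed parameters. The synopsis also describes the run-in as a session "in which the parameters and procedures will be a replica of the study".

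**What happens to Part 1 data.** There are three kinds of statement.

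- *Excluded.* Section 5.6, after saying that women in both parts undergo the same procedure, continues: "however, results will not be collected or recorded for analysis from Part 1 of the study". Section 3.3: "The results of the run-in pilot study will not be included in the results and data analysis". Synopsis (Procedures/Methods): "these results will not count towards the documented results".
- *Recorded.* Section 5.7 has ultrasound and case data collected for every subject. Section 6.6 has the operator enter the research and reference FHR values on the CRF. Section 6.7 has images, which carry the scan parameters, saved for each subject scanned. None of the three exempts Part 1.
- *Possibly analysed.* Synopsis (Objectives): "Data from Part 1 and Part 2 may be pooled or analyzed as separate subgroups, as determined necessary by the sponsor".

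**The concern.** Part 1 is the only place where the accuracy method is to be defined. Section 10.8 names no agreement statistic, limit or accuracy calculation, and section 10.6 states that no hypothesis is tested. The primary objective is nevertheless to validate accuracy. So the choices made in Part 1 determine what the Part 2 result will mean.

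The study is open-label and run at the sponsor's own facility. Its only listed bias control is consecutive enrolment (section 1.3), and the sponsor may look at the data at any time (section 10.8.1). In that setting an outside reader needs to see what the accuracy calculation was based on and when it was fixed. The protocol does not say clearly that the Part 1 evidence is kept, and it does not ask for a record of the decision.

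The pooling sentence raises the reverse risk. If Part 1 data help to choose the parameters and the calculation and are then added to the accuracy result, the validation is no longer independent of the choices it is meant to test.

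**Working it through.** The documents give no alpha, power, SD or margin, so there is no stated figure to reproduce. The check is a comparison of the text, followed by a count of what is at stake.

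**Step 1. The statements side by side.**

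| Question | One answer | Another answer |
|---|---|---|
| Are Part 1 results recorded? | 5.6: not collected or recorded, qualified by *for analysis* | 5.7, 6.6, 6.7: collection and recording, no Part 1 exception |
| May they enter the analysis? | 3.3 and 5.6: no; synopsis (Procedures/Methods): do not count | Synopsis (Objectives): may be pooled or shown as a subgroup |
| Are the parameters settled in Part 1? | Synopsis (Procedures/Methods): already a replica of the study | Synopsis (Research Type) and 3.3: to be determined there |
| What record supports the choices made? | None specified | None specified |

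**Step 2. Where each reading leads.**

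- Section 5.6 read literally, as a specific exception to the general recording rules: a site could retain nothing, and the accuracy method would have no evidence on file.
- Section 5.6 read as exclusion from the analysis set only: the data exist, but choosing parameters and a calculation from them is itself a use of the results, and that use is left undescribed.
- Synopsis pooling sentence followed: Part 1 data can both shape the method and count in its validation.

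**Step 3. How many pairs are involved.** Section 5.7 has 8 paired scans attempted per woman. Table 1 and section 10.7 allow up to 5 women in Part 1. The synopsis gives 3 volunteers per session, and I assume the run-in session has the same number.

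- Part 1: 3 × 8 = 24 pairs, to 5 × 8 = 40 pairs, if every attempt succeeds.
- Part 2: 15 × 8 = 120 pairs (Table 1), or 20 × 8 = 160 pairs (section 10.7).
- Share from Part 1 if pooled at maximum enrolment: 40/(40 + 120) = 25%, or 40/(40 + 160) = 20%.

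**Step 4. What Part 1 could say about spread.** Within-woman degrees of freedom are 3 × 7 = 21 and 5 × 7 = 35. The 95% limits for true over estimated SD are √(df/χ²), using the upper and lower 2.5% points of χ²:

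- df 21: 0.77 to 1.43
- df 35: 0.81 to 1.30

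These limits assume independent differences of equal variance under stable conditions. In Part 1 the parameters are still being settled and operators may have any experience level. Part 2 has fixed parameters and about 4 novice operators and 1 experienced. The limits are therefore optimistic as a forecast for Part 2.

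**The case against.** The strongest reply is that section 5.6 says *for analysis*. On that reading it only keeps Part 1 out of the analysis dataset, which is how section 3.3 puts it. Recording is required elsewhere without exception for Part 1. Section 11.6.3 has source documents retained for each subject, and section 11.6.4 has all study data archived for at least 3 years. The pooling sentence itself presupposes that Part 1 data exist.

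Much of this stands. A reader might infer that the protocol forbids recording Part 1 data, that nothing from Part 1 is kept, and that Part 1 therefore cannot do its job. The documents do not support that: sections 5.7, 6.6 and 6.7 point the other way, and 5.6 carries its qualifier. A reader might also infer that the accuracy method will be chosen to favour the device. The text shows only that such a choice could not be ruled out from the record.

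Three things survive the reply. Section 5.6 goes beyond 3.3 by speaking of collection and recording, and it does so as a contrast between the parts, so a site could take it as the specific exception. The exclusion in 3.3 and 5.6 cannot be squared with the pooling sentence on any reading. And no section says what Part 1 evidence, criterion or dated record must support the chosen parameters and accuracy calculation.

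It is also fair to say that a study with no hypothesis and no power calculation need not state its Part 2 precision in advance. The SD figures are therefore a minor benefit of keeping the data, and the point does not depend on them.

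**Conclusion.** The point holds as an internal contradiction with a missing safeguard. The protocol gives incompatible answers on whether Part 1 data are recorded and whether they may be analysed, and it requires no documented Part 1 basis for the choices that define the accuracy result. Either the evidence behind the method may not be retained, or the data used to choose the method may enter its validation.

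In size, 24 to 40 pairs are affected, and at maximum enrolment 40 pairs would be 20% to 25% of a pooled dataset. This assumes 8 successful pairs per woman and, for the lower count, 3 women in the run-in. The shares measure exposure; the documents give nothing from which a bias in the accuracy result could be computed. Any SD from Part 1 is only a rough guide to Part 2. The wording should be corrected before Part 2 starts.

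**What to change.** 1. Replace the section 5.6 sentence with: *Part 1 Vscan and reference FHR values, scan settings, attempts and operator are recorded on CRFs marked run-in and retained. They are used to fix the Part 2 parameters and the accuracy calculation, and are not included in the Part 2 accuracy result.* Operator and failed attempts are not in the section 6.7 CRF list, so they need to be added.
2. Delete the pooling sentence in the synopsis, or limit it to a separate descriptive listing of Part 1.
3. Require the chosen parameters and accuracy calculation, with the Part 1 data supporting them, to be documented and dated before the first Part 2 scan.
4. Limit the replica wording in the synopsis to the subject procedure.

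Items 1 and 2 belong together: changing 5.6 alone would leave it in conflict with the synopsis. Item 3 makes the choices checkable, which extra CRF rows alone would not.

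The cost is protocol wording, a short dated decision record, and 24 to 40 CRF rows. No extra subjects, scans or staff are needed. The sponsor gives up the option of pooling Part 1 into the accuracy result.
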